#### 7.5 Multiple Testing

We will not formally control for multiple comparisons since the aim of this trial is to identify cLBP patient phenotype and treatment combinations for future study. Additionally, we would have little power to identify significant phenotype-treatment interactions with multiple testing procedures due to the study design (16 possible SMART treatment pathways, 12 dynamic treatment regimens and n=408 patients) and heterogeneous patient phenotypes. Results will be presented using confidence intervals and standardized treatment effect sizes rather than p-values. We will additionally employ cross-validation schemes when appropriate to assess the degree to which phenotype-treatment interactions generalize out-of-sample.

### 8 Summary of Study Data

A CONSORT flow diagram (Appendix A) will compare how the study unfolded with the pre-trial plan to include information about the number screened, the number enrolled, the number randomized to each intervention at each stage of the trial, final completion rates, and the number of individuals in analytic datasets.

We will use descriptive statistics to assess data quality and characterize relationships between phenotype features prior to each treatment. In preparation for the main multivariate model-based

analysis we will look at correlations between phenotype variables and responses with correlation analysis and scatterplots, analyze data for evidence of collinearity between factors, study patterns of missing data, and conduct univariate analysis using models described below. The goal of the data summarization is to elicit a good feel for the specific data in our team of analysts and to guide an initial approach to data reduction and predictive model trimming.

At first, all intervention groups will be combined. Any variable that requires creation from collected data will be coded and created for examination. Continuous variables will be summarized by minimum, maximum, arithmetic mean, median, and standard deviation at each time point. Histograms and boxplots will be used to assess distributional characteristics of baseline and follow-up variables. The outcomes will be summarized and plotted at each time of assessment to assess distributional characteristics. Categorical variables will be tabulated with frequencies and percentages. The number and percentage of missing observations for all variables will be reported for each variable at each time point for the entire sample. Missingness for the primary and secondary outcome variables will be assessed by intervention group to evaluate any differential missingness.

We will then describe the patient population by initial intervention group to construct a table describing the baseline characteristics of each intervention group. The table will include baseline characteristics, baseline medical history, and baseline values of primary and secondary outcome variables. Significance testing of baseline characteristics between groups will not be performed based on statistical and CONSORT recommendations.

## **8.1 Subject Disposition**

A patient will be considered to have reached stage  $t$  after they complete the patient reported outcome forms within the specified stage  $t$  window. A subject will be considered to have dropped out of the study at stage  $t$  if they progressed to the prior stage but fail to complete the patient reported outcome forms within the stage  $t$  window. Whenever possible, the reason for each subject's dropout will be recorded. See Protocol for details concerning the timing of study assessments.

The full analysis population consist of all subjects who complete the patient reported outcome forms at stage T2 at the end of the run-in phase. The full analysis population size will be a count of these patients. The per-protocol analysis populations will consist of all patients who remain in the study and are complaint with their treatment assignments during the first and second treatment periods. The per-protocol population sample size will equal the number of patients who complete the study to stage T4 and are compliant with treatment. Treatment compliance is defined in Section 9.5.

Subjects will be recruited into the study over the course of 2.5 years. Target recruitment rates vary by month based on historical recruitment averages at the BPC. On average, the study aims to recruit 10-15 subjects per month.

## **8.2 Derived variables**

The study's primary and secondary endpoints are each scored as recommended by instrument authors. The PROMIS-based measures will be derived in Qualtrics using a tool released by HealthMeasures.net. The PROMIS composite scores have a population mean and standard deviation equal to 50 and 10 points, respectively. The Oswestry Disability Index is calculated by summing the individual item scores (values ranging from 0 – 5) and multiplying by 2. Its range runs from 0 to 100.

### 8.3 Protocol Deviations

An accidental or unintentional change to, or non-compliance with the research protocol that does not increase risk or decrease benefit or; does not have a significant effect on the subject's rights, safety, or welfare; and/or on the integrity of the data. Deviations may result from the action of the subject, researcher, or research staff's departure from the IRB approved research protocol without prior IRB approval for the variation. Missing data are part of protocol deviations and may lead to exclusion from the per-protocol analysis population.

Participant-specific protocol deviations will be assessed for their potential relationship to the treatment effects or the course of the disease by a medical expert. Since deviations because of safety will generally result in incomplete data on the subject, their consequences will be handled in the analysis as potentially informative missing data (see Section 8.4). Due to the difficulty of accurate determination of the relationship between protocol deviations and the treatment efficacy and the disease dynamics, several versions of the primary and secondary analysis will be undertaken:

1. Exclusion of the violators from the analysis population under the missing at random assumption.
2. If missing data fraction exceeds 15%, multiple imputation of the violator's unobserved responses using predictive matching algorithms, including the per-protocol analysis of the resultant imputed population(s).
3. With yes/no responses that have the meaning of success or failure where mixed logistic models are used per protocol, violator's responses will be classified as failures for the conservative analysis.
4. Analytic methods (2,3) applied only to violators classified as treatment or disease-related as defined by medical experts.

### 8.4 Demographic and Baseline Variables

The following patient-level variables will be collected at T1 and will be treated as demographic variables during the primary and secondary analyses. There are no planned transformations of the baseline variables.

- Age
- Sex
- Gender identity
- Ethnicity
- Race
- Education level
- Employment status
- Marital status
- Household size

Summary statistics will be produced in accordance with section 9.

### 8.5 Treatment Compliance

Treatment compliance for each of the four study treatments is defined below in Table 4.  
*Table 4 Compliance standards for treatments*

Treatment	Compliance Standard
MBSR	Completion of 4 out of 8 sessions
PT/Exercise	Completion of 80% of PT sessions

Acupressure	Completion of 70% of the 30-minute sessions.
Duloxetine	Compliance will be assessed by counting pills returned to research pharmacy.

## 9 Analysis Plan

### 9.1 Objective 1 Analysis Plan

**Objective 1:** Assess differential treatment response using the light and deep phenotype data. The main hypotheses of Objective 1 will be addressed by fitting a joint regression model the primary pain outcome (PROMIS pain interference score) at time point T3 which gains efficiency by incorporating observations at time point T4. The purpose of this analysis is to demonstrate that clinical measures are capable of predicting differential responsiveness to the four cLBP treatments. This analysis will assess the degree to which the clinicians' hypothesized treatment modifiers predict differential treatment response. Testing the differential treatment response hypotheses will be handled by including treatment-phenotype interactions in the model. The analysis will be repeated for the secondary pain outcomes (Pain intensity (PEG) and Patient Global Impression of Change (PGIC)).

#### 9.1.1 Light Phenotyping Analysis

Let  $Y_{ti} \in \mathbb{R}$  denote subject  $i$ 's PROMIS pain interference score at time  $t \in \{2, 3, 4\}$ . Let  $R_i$  denote response status at T3. Let  $A_{ti}$  be a vector denoting treatment assignment, such that the first through 4th elements represent PT/Exercise, MSBR, Acupressure, and Duloxetine treatment status. The vector  $X_{2i}$  contains the baseline covariates for subject  $i$  at time 2 (sex, age, BMI, race, and education) and  $Y_{2i}$ . For  $t \in \{2, 3\}$ , the matrix  $Z_{ti}$  will hold subject  $i$ 's time  $t$  measurements of the hypothesized treatment modifiers.  $Z_{ti}$  will have 7 total columns that correspond to the hypothesized treatment modifiers, and the columns will be specified such that the element-wise product  $A_{ti} \cdot Z_{ti}$  represents the 8 hypothesized treatment-phenotype interactions.

We jointly model data at T3 and T4 to gain efficiency in estimating the main effects of treatment, the main effects of the potential moderators, and the interaction effects between treatment and the potential moderators in stage 1. The main effects of treatment and covariates are allowed to differ between stages, but we assume these effects are additive. In contrast, treatment-by-phenotype interaction effects are assumed to be the same across both stages. We propose the following model:

$$\begin{aligned} E[Y_{3i}] &= X_{2i}^T \beta_2 + A_{2i}^T \phi_2 + Z_{2i}^T \varphi_2 + (A_{2i} \circ Z_{2i})^T \psi_2 \\ E[Y_{4i}] &= X_{2i}^T \beta_2 + A_{3i}^T \phi_2 + Z_{3i}^T \varphi_2 + R_i^T [A_{3i}^T \phi_{3R} + Z_{3i}^T \varphi_{3R}] \\ &\quad + (1 - R_i)^T [A_{3i}^T \phi_{3NR} + Z_{3i}^T \varphi_{3NR}] + (A_{3i} \circ Z_{3i})^T \psi_2 \end{aligned}$$

We will fit the model for all repeated measures ( $Y_{3i}, Y_{4i}$ ) using generalized estimating equations (GEE) with a working independence covariance matrix through the R package *gee*. We will use robust standard errors for variance estimation to account for the use of repeated measures. Prior to conducting inference, we will assess the functional forms of the predictors and the validity of the assumptions required for joint stage modeling, especially the assumption of constant interaction effects across treatment stages. If the assumptions for joint modeling are violated, we will conduct the primary analysis with stage 1 data only. For inference, we additionally assume  $Y_{3i}, Y_{4i}$  follow a multivariate normal distribution.

The clinical objective of Aim 1 is to show that patient responsiveness to treatment depends on their

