12.1 Mini-Assessments

Participants will also be asked to complete electronic questionnaires every 2 weeks throughout the study. There are a total of 17 mini-assessments and those in weeks 1, 6, 15, 24 and 36 will be completed as part of the study visit survey (T1-T5). There will be 12 additional mini-assessments will take place at weeks 3, 8, 10, 12, 17, 19, 21, 26, 28, 30, 32 and 34. There are three types of mini-assessments- standard, expanded and mediation and these are described below.

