13.5 Lodging

Patients traveling from more than 60 miles may be offered lodging for their study visits.

14 Post-Intervention Assessments (T2-T5)

Participants will be scheduled for a return visit immediately before and after each intervention period (T2, T3, and T4) and at 3 months after the final scheduled treatment period (T5). These visits can occur virtually or as a hybrid visit combining online and in-person data collection. At the follow-up, changes in medications will be elicited and cross-referenced to the EMR, with an emphasis on use of opioids, new diagnoses, and other interventions. The effect of adherence on outcome will be explored. Data maybe

Study Activity	Payments
All Participants	\$600
Study visits (5 total)	\$40 (\$200)
Blood draw	\$10
Vitals and physical exam	\$50
MRI	\$90
Hospital parking	\$5
Symptom monitoring (EMA-5 total)	\$15 (\$75)
Mini-assessments (12 total)	\$10 (\$120)
Completion of 1 st treatment	\$50
Optional Deep Visits	\$500
Study visits (2 total)	\$100 (\$200)
fMRI and blood draw (2 total)	\$145 (\$290)
Hospital parking (2 total)	\$5 (\$10)
Unscheduled Deep Visit Triggered by Non-Study Intervention	\$260
Study visit	\$100
fMRI and blood draw	\$145
Follow-up surveys (2 total)	\$5 (\$10)
Hospital parking	\$5
Unscheduled Non-Study Intervention Follow-up	\$10
Follow-up surveys (2 total)	\$5 (\$10)

collected in one of two ways; by either an in person at the Back & Pain Center or done remotely through a virtual platform. There is also a series of 12 brief online mini-assessments interspersed within the light and deep phenotyping visits, such that participants will have key PROs collected every 2 weeks for the study period (see Section 12.1 for mini-assessments and section 1.3 for specific questionnaires being collected at each time point).

15 Retention

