## 5 Study Methods

### 5.1 General Study Design and Plan

We will conduct a 36-week pragmatic trial in a cohort of cLBP patients (see Figure 1 and Figure 2). The proposed SMART will consist of a 4-week run-in period using an online cognitive-behavioral self-management intervention (PainGuide), followed by two 8-week treatment periods. All participants will be followed for a total of approximately nine months.

At baseline (T1), approximately 500 patients will undergo a comprehensive baseline phenotyping assessment. After receiving PainGuide (access to an online self-management program) for 4 weeks, each participant will complete a light phenotyping assessment (T2) and a subset of these patients (n=160) will complete an additional deep phenotyping assessment. Those who still have significant pain interference ( $\geq 2$  from Patient Global Impression Scale, PGIC) will be randomized to one of the four 8-week long interventions (i.e., Mindfulness-Based Stress Reduction (MBSR), Physical Therapy (PT)/Exercise, Acupressure self-management [eHealth app], or Duloxetine). Participants with a PGIC=1 will not be randomized and continue with long-term follow-up. The PainGuide run-in is designed to provide the lightest “touch” intervention and to help control for regression to the mean. We will use block randomization with random block size of 4 and 8. Approximately 102 patients will be assigned to each treatment group including Physical Therapy/Exercise, MBSR, Acupressure, and Duloxetine treatment groups. For addition details, please see Section 6.3.

Following the first 8-week treatment period, patients will be reassessed (T3) using light only or light plus deep assessments (for the subset of 160) and those still having significant pain interference ( $\geq 2$  from Patient Global Impression Scale [PGIC]) will be re-randomized to receive one of the three treatments they did not receive in the first treatment period. Participants with a PGIC=1 will not be randomized and continue with long-term follow-up. After the second intervention and three months later, all undergo the light phenotyping follow-up assessment protocol (T4). Lastly, a final assessment will take place at 3 months after the scheduled end of the second 8-week treatment period (T5). There will also be a series of interim assessments that take place at 2-week intervals in between the regular assessments (T1-T5).

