#### **5.4.2 Inclusion Criteria for Light Phenotyping**

- We will use the definition of chronic low back pain (cLBP) described in the NIH Task Force Report on Research Standards for Chronic Low Back Pain, i.e. low back pain present at least six months, and present more than half of those days.
- Individuals must have a pain interference score of  $\geq 60$  on PROMIS Pain Interference at T1 for inclusion. The normal population mean and standard deviation for the PROMIS Pain Interference measures are 50 and 10 points, respectively. Therefore, participants must be 1 SD above the population mean ( $>=60$ ) for inclusion.
- Individuals must be willing and eligible to be randomized to receive at least three of the four proposed treatments.

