## Statistical Analysis Plan

Force Minimum Dataset*																				
Low Back Pain-Specific Pain Intensity*		X		X	X			X	X			X			X	X	X	X	X	X
Opioid use- Single-Item Current Opioid Use*		X		X	X			X	X			X			X		X			
Pain Intensity (PEG)*		X			X				X			X			X		X			
PROMIS Physical Functioning 6b*		X		X	X			X	X			X			X	X	X	X		
PROMIS Anxiety 4a*		X		X	X			X	X			X			X	X	X	X		
PROMIS Depression-4		X		X	X			X	X			X			X	X	X	X		
PROMIS Fatigue		X		X	X			X	X			X			X	X	X	X		
PROMIS Sleep Disturbance 6a*		X		X	X			X	X			X			X	X	X	X		
Sleep Duration*		X		X	X			X	X			X			X	X	X	X		
PROMIS Social Role Activity		X		X				X				X			X	X	X	X		
PROMIS Pain Interference 4a*	X	X		X	X			X	X			X			X	X	X	X	X	X
PROMIS Cognitive Function		X		X	X			X	X			X			X	X	X	X		
PROMIS Pain intensity		X		X	X			X	X			X			X	X	X	X	X	X
Pain Catastrophizing Scale (PCS)*		X		X	X			X	X			X			X		X			
Patient Health Questionnaire-2 (PHQ-2)*		X			X				X								X			

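### The primary model leaves out the T1 and week-3 pain scores taken before randomisation, and its T4 equation has no term for a first-treatment moderator effect that persists into stage 2

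*SAP*

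**What the plan says.** In SAP section 9.1.1 the covariate vector X_2i holds the patient's values "at time 2 (sex, age, BMI, race, and education) and" Y_2i, the T2 pain interference score. The same vector, with the same coefficients, enters the equations for T3 and T4. In the T4 equation the modifiers are updated to their T3 values (Z_3i) and response status R_i is added. The pain score stays at T2.

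The score is collected more often than that. The "PROMIS Pain Interference 4a" row of SAP Table 1 (section 5.6) is marked at T1, T2, T3, T4 and the mini-assessments. T1 is certain to exist, because eligibility rests "on PROMIS Pain Interference at T1 for inclusion" (SAP 5.4.2). Protocol 12.1 says "12 additional mini-assessments will take place at weeks 3, 8, 10" and so on, and T2 is at week 6. Protocol section 14 adds that "participants will have key PROs collected every 2 weeks for the study period".

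Two further statements matter for stage 2. SAP 5.1 says patients with continuing pain "will be re-randomized to receive one of the three treatments they did not receive in the first treatment period". SAP 9.1.1 says "treatment-by-phenotype interaction effects are assumed to be the same across both stages", so a single coefficient vector ψ serves T3 and T4. As printed, the T4 equation contains the second treatment (A_3i) but neither the first treatment (A_2i) nor its product with the T2 modifiers. SAP 9.2 does adjust T4 for first treatment, but only in the exploratory Objective 2 model and only as a main effect.

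**The concern.** There are two separate matters.

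The first is precision. One four-item score is a noisy measure of where a patient started. Two earlier readings of the same instrument are in the data set and precede randomisation. The SAP pools T3 and T4 to gain efficiency, and in section 7.5 it concedes limited power for interactions. Leaving collected prognostic scores out works against that aim.

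The second is the stage-2 contrast. Patients on treatment k in stage 2 never had k in stage 1, but some of the patients they are compared with did. If a first-treatment moderator effect is still present at T4, it appears only in the comparison group and makes the stage-2 interaction look smaller. No washout is described: T3 is at week 15 and, on the Table 1 timetable, the second treatment starts the week after. Some carryover is therefore plausible. What is at stake is a pull toward zero in the pooled ψ that the Wald tests use.

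**Working it through.** **The plan's own figure.** SAP 6.1 claims at least 80% power for r = 0.28 with n = 102, two-sided 5%. Fisher's z gives Φ(atanh(0.28)·√99 − 1.96) = Φ(2.862 − 1.96) = 81.7%. The claim reproduces.

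**Step 1: T1 and week 3.** The documents give no correlations between visits, so these are assumed.
- With equal correlation ρ between visits, residual variance given k earlier scores is 1 − kρ²/(1 + (k−1)ρ). At ρ = 0.5, T2 alone leaves 0.750 and three scores leave 0.625, a ratio of 0.833. For ρ from 0.4 to 0.8 the ratio runs from 0.873 to 0.726.
- T1 is cut off at 60 by eligibility, which weakens it. With that truncation the ratio is about 0.88 at ρ = 0.5 and 0.80 at ρ = 0.7.
- With a stable trait, a decaying component and noise (T2–T3 correlation 0.39 to 0.55, T1 truncated), the reduction is 3 to 11%.
- Under an exact AR(1) process the ratio is 1.00, because T2 then carries everything.

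In patients, 408/0.97 − 408 ≈ 13 and 408/0.89 − 408 ≈ 50. On the SAP's own power scale, dividing 2.862 by the square root of the variance ratio moves 81.7% to 82.8% (ratio 0.97), 85.9% (0.89) or 89.3% (0.80). This is a translation of precision. The SAP gives no power for the interaction test itself.

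**Step 2: stage-2 shrinkage.** With equal allocation and everyone re-randomised, P(first = k | second = k) = 0 and P(first = k | second ≠ k) = (1/4)/(3/4) = 1/3. If a share c of ψ persists, the modifier slope in the comparison group rises by cψ/3. The contrast becomes ψ − cψ/3 = ψ(1 − c/3).

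A one-modifier version of the model was fitted to 1,000,000 simulated patients. The table shows the T4 interaction as a ratio to truth. The last column is the pooled T3+T4 estimate from the printed model. In the transition process the stage-1 effect reaches T4 through the T3 score. In the trait-plus-noise process it does not.

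| Process | c | 1 − c/3 | Printed | + T3 score only | + A_2, A_2×Z_2 | + all three | Pooled, printed |
|---|---|---|---|---|---|---|---|
| Transition | 0 | 1.000 | 0.998 | 0.998 | 0.998 | 0.998 | 1.002 |
| Transition | 0.3 | 0.900 | 0.901 | 1.003 | 0.999 | 1.000 | 0.955 |
| Transition | 0.5 | 0.833 | 0.834 | 1.005 | 0.999 | 1.003 | 0.917 |
| Transition | 0.7 | 0.767 | 0.779 | 1.012 | 1.007 | 1.010 | 0.888 |
| Trait + noise | 0 | 1.000 | 1.003 | 1.109 | 1.007 | 1.005 | 1.007 |
| Trait + noise | 0.5 | 0.833 | 0.830 | 0.943 | 0.996 | 0.996 | 0.913 |
| Trait + noise | 1 | 0.667 | 0.660 | 0.775 | 0.993 | 0.990 | 0.824 |

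With 12% not re-randomised, the printed T4 ratios in the transition process at c = 0.3, 0.5 and 0.7 are 0.92, 0.87 and 0.81, and the pooled ratios are 0.97, 0.94 and 0.91.

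**Step 3: why all three terms.** The T3 score alone is right only if carryover runs through it; otherwise it over- or under-corrects. A main effect of first treatment alone leaves the shrinkage unchanged. A_2 and A_2×Z_2 without the T3 score drift to 1.05 if the modifier is only partly stable between T2 and T3 (stability 0.7, c = 0.5, transition process). With the T3 score added the ratio is 1.005. The T2 slope must also be freed: given the T3 score, T2 has a different coefficient at T4, and forcing one slope left the pooled estimate at 0.95 to 0.99 of truth even in the transition process.

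**The case against.** Adjusting for T2 alone is standard and valid. The endpoint is change from T2 to T3, and SAP 5.1 says the run-in is there partly to limit regression to the mean. The precision gain rests on correlations the documents do not report and could be nil. At stage 2 the model already carries T3 information through R_i and Z_3i. SAP 9.1.1 also plans to check that interactions are constant across stages and to use stage 1 alone if they are not.

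Much of this stands. The T1 and week-3 scores improve a valid analysis, and their value is uncertain until the data are seen. The constancy check is weaker protection. At c = 0.5 and ψ = 0.28 SD the stages differ by 0.28 × 0.5/3 = 0.047 SD, below the simulated pooled standard error of about 0.068 at N = 408. Such a difference would usually go unnoticed.

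A reader might infer more than the documents support, in three ways.
- That leaving out the T3 score itself biases the stage-2 interaction. It does not: omitting a prognostic score from a randomised linear model causes no such bias. The shrinkage comes from re-randomising away from the first treatment with no A_2×Z_2 term, and it needs carryover.
- That adding the T3 score alone makes the estimate unbiased. The trait-plus-noise rows show otherwise.
- That a large power gain in a T4-only test is at stake. The SAP plans no such test. In the pooled estimate, adding the T3 score did not lower the standard error (for example 0.0683 to 0.0700).

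**Conclusion.** The omission of the T1 and week-3 scores is a fact of the text. Using them is a nearly free gain: no bias to the randomised interaction, and 3 to 11% less stage-1 residual variance under moderate assumed correlations, with a range from zero (exact AR(1)) to about 20% (higher correlations, T1 truncated).

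The stage-2 point is conditional. If a share c of a first-treatment moderator effect persists to T4, the stage-2 interaction is about ψ(1 − c/3) and the pooled estimate loses about half that amount: roughly 4 to 11% for c from 0.3 to 0.7 with everyone re-randomised, somewhat less with 12% responders. With no carryover there is no loss. The T2-to-T3 estimate, which is the primary endpoint, is not shrunk in any case.

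The gain from the fuller T4 equation is mainly in bias. At c = 0.5 the printed effect relative to its standard error is 0.92 of the ideal. With the fuller equation it is between 1/1.06 = 0.94 and 1/1.03 = 0.97. At c = 0.3 the two are about level (0.955 against 0.94 to 0.97).

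**What to change.** Add the T1 and week-3 pain interference scores to X_2i in SAP 9.1.1, with a simple covariate imputation, blind to treatment, where week 3 is missing. This needs no new data and costs two coefficients.

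If T4 is pooled with T3, add three things to the T4 equation together: first treatment (A_2), its product with the T2 modifiers (A_2×Z_2), and the T3 score with its own coefficient. Let the coefficient of the T2 score differ between the two equations. Do not add the T3 score by itself.

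The price of the T4 change is a pooled standard error about 3 to 6% larger than under the printed model. The regimen means in SAP section 11 also need one more step, averaging predictions over the T3 score, because that score is itself affected by the first treatment. A sponsor unwilling to pay this could make the stage-1 model primary and report the pooled model as supportive.
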